The clinical effects of riboflavin supplementation on psoriasis were first explored in the 1950s. In 1952, [name] published a case series of 148 psoriasis patients he had injected with 5-10 mg of riboflavin intramuscularly once weekly and then followed clinically. Of those 148 patients, 24% had complete remission (“healed”), and 68% had at least a 50% improvement. Only 7% of the patients failed to respond or had less than a 50% improvement. Maynard also sent surveys to 156 of his psoriasis patients that he had treated with riboflavin but whom he had not seen in clinic for two years. He received 50 survey cards back and, of those cards, 82% of patients reported they had “healed,” “improved with no relapse,” or “improved with partial relapse.” Only 18% of responders felt their disease was the same as before riboflavin treatment.

Maynard’s work was soon followed by other publications on the topic. In 1952, Sulzberger and Baer published their observations that riboflavin 30 mg by mouth daily did not help psoriasis. In contrast, in 1954, Italian investigators Montilli and Pisani reported that daily intramuscular injections of 10 mg of riboflavin either clinically cured or improved the disease in 33 out of 42 psoriasis. In 1956, [name] published a case series demonstrating that weekly intramuscular injections of 50 mg of riboflavin for 4 to 16 weeks “improved” or “markedly improved” 39 out of 44 psoriatic patients in his clinic. In contrast, in 1957, Drs. Welsh and Ede published a large case series of 348 psoriasis patients they treated with riboflavin and concluded “moderate and/or massive dosages” of riboflavin

**Title:** The Effect of Riboflavin on Moderate to Severe Plaque Type Psoriasis  
**Principal Investigator:** [name]

failed to produce any significant response in those patients. To our knowledge, there have been no more published trials or case series on the clinical effects of treating psoriasis with riboflavin. Taken together we think the results of these trials are intriguing and create clinical equipoise on whether riboflavin is an effective treatment for psoriasis.

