### 4 STUDY DESIGN

A 28-week, double-blind, placebo-controlled, prospective study with cross-over of both the riboflavin and placebo groups at the 12-week time mark.

Patients will take either 400 mg of riboflavin (“B2-400”) or a placebo by mouth once a day for 12 weeks. There will be a four week wash-out period at week 12 as the groups cross-over.

We propose using a 400 mg daily dose in this clinical trial as there is the most evidence in previous human studies for a clinical effect with this dose. While data suggesting equivalent activity of riboflavin at a lower dose is intriguing, we feel it is premature to choose a lower dose based off the findings in one trial that was stopped prematurely.

Up to 50 subjects will be enrolled. Six skin biopsies will be performed to measure metabolomics profiles, and there will be five blood draws to measure serologic markers.

**Title:** The Effect of Riboflavin on Moderate to Severe Plaque Type Psoriasis  
**Principal Investigator:** [name]

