## **11 STATISTICAL METHODS**

A block randomization schedule will be created and all subjects randomly assigned to a sequence of treatment and dispensed study product. Assuming a large effect size and a conservative amount of correlation between the measurements, a sample size of 22 subjects in each sequence yields a statistical power of 80%.

All clinical and laboratory assessments will be descriptively summarized at each visit (weeks 0, 2, 12, 16, 18, and 28) for the modified intent-to-treat population. Continuous variables will be summarized with standard descriptive statistics including mean, standard deviation and range. Categorical variables will be summarized by frequency and percentage (N, %).

Differences within each sequence of treatment from baseline to endpoint will be assessed using parametric general linear models such as the paired t-test. The two sequences will also be compared with respect to dichotomized improvement from baseline to the 12-week visit for key clinical endpoints using the McNemar test. Assuming no carryover effects due to the four-week washout period, all data will be pooled and used to estimate the treatment effect. An analysis testing the assumption of equal carryover effects will be performed. Wilcoxon signed rank test will be used to compare ordinal or nominal assessments. Parametric t-tests will be used to determine if continuous laboratory assessments are significantly different between the treatment groups.

**Title:** The Effect of Riboflavin on Moderate to Severe Plaque Type Psoriasis  
**Principal Investigator:** [name]

An overall alpha-level of 0.05 will be used to determine statistical significance and all statistical tests will be two-sided. All data will be analyzed using SAS (SAS Institute, Inc., Version 9.3) software.

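### Pooling assumes no carryover, and a non-significant result from the plan's unspecified carryover test would not validate that assumption

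*Combined protocol and SAP*

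**What the plan says.** Section 11 (Statistical Methods) states the basis for the pooled estimate: "Assuming no carryover effects due to the four-week washout period, all data will be pooled and used to estimate the treatment effect". The next sentence gives the check: "An analysis testing the assumption of equal carryover effects will be performed". The plan does not say which statistic is meant, what size of carryover it should detect, or what happens if it rejects. The general rules are "An overall alpha-level of 0.05 will be used to determine statistical significance" and "all statistical tests will be two-sided"; no separate level is set for carryover.

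On size, Section 11 says "a sample size of 22 subjects in each sequence yields a statistical power of 80" percent, for a large effect and a conservative correlation, neither with a number. Section 4 caps enrolment: "Up to 50 subjects will be enrolled".

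Three other statements matter here:
- Section 6.3 (item 9) makes week 16, after the washout, the baseline for the second period. Table 1 schedules PASI at that visit.
- Section 11 also compares the two sequences on dichotomised improvement at week 12, naming McNemar's test.
- Section 2 says that riboflavin is not stored in the body. It also reports an uncontrolled survey of patients not seen in clinic for two years, with 50 cards returned out of 156, in which "82% of patients reported they had" healed or improved. That figure includes improvement with partial relapse.

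**The concern.** A two-period crossover gains its precision by comparing each subject with themselves. The second period is a clean comparison only if what remains of the first treatment is the same in both sequences. The plan assumes this and offers one test as a check.

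If that test has little power, it will usually be non-significant whether or not carryover is present. A reader of the report could then take a quiet result as support for the pooled estimate. Because the plan states no consequence for either result, nothing in it guards against that reading. At stake is whether the main treatment estimate can be interpreted if riboflavin has an effect on plaques that outlasts the dosing.

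**Working it through.** **Inputs from the documents.** 22 per sequence (44 in total), two-sided alpha 0.05, four-week washout, week-16 re-baselining.

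**Assumptions, because the documents give no figures.** A large effect is d = 0.8. Carryover is 0.2, 0.4 (half the effect) or 0.8 SD (the whole effect). The within-subject correlation rho runs from 0 to 0.7.

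**1. The plan's own figure.** The stated power, "yields a statistical power of 80" percent, cannot be reproduced uniquely. With d = 0.8 and 22 per sequence:
- unadjusted comparison of two parallel groups: 74% (t) or 76% (normal)
- baseline-adjusted comparison at rho = 0.35: 79% or 81%
- mean of two measures at rho = 0.7: 80%
- within-subject crossover: 96% at rho = 0, above 99% at rho = 0.5

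So 80% is attainable under some choices but cannot be confirmed. No power is stated for carryover.

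**2. Test on subject totals.** This is the standard two-period form, comparing each subject's sum over both periods between sequences. In SD units, SE = sqrt(2 × 2(1 + rho)/22). Power is from the noncentral t with 42 df.

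| rho | SE | Power, 0.2 SD | Power, 0.4 SD | Power, 0.8 SD | 95% CI half-width (2.018 × SE) |
|---|---|---|---|---|---|
| 0 | 0.426 | 7.4% | 15.0% | 45.0% | 0.86 |
| 0.3 | 0.486 | 6.9% | 12.7% | 36.3% | 0.98 |
| 0.5 | 0.522 | 6.6% | 11.6% | 32.2% | 1.05 |
| 0.7 | 0.556 | 6.4% | 10.8% | 29.0% | 1.12 |

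With 25 per sequence (the cap of 50, if balanced), 0.4 SD at rho = 0.5 gives 12.6%. At that correlation, 80% power needs 4(1.5)(1.960 + 0.842)²/0.4² ≈ 295 per sequence for 0.4 SD, or about 74 for 0.8 SD.

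A simulation of the total of two binary PASI 50 responses, with assumed rates of 40-50% on riboflavin and 10-20% on placebo, gives about 10-15% power when carryover is half the effect. It gives about 25-45% when carryover equals the effect.

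**3. Comparison at week 16, before second-period dosing.** SE = sqrt(2/22) = 0.302 unadjusted, or sqrt(2(1 - rho²)/22) adjusted for week 0.

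| Analysis | Power, 0.4 SD | Power, 0.8 SD |
|---|---|---|
| Unadjusted | 25% | 74% |
| Adjusted, rho 0.3 | 27% | 78% |
| Adjusted, rho 0.5 | 32% | 85% |
| Adjusted, rho 0.7 | 44% | 95% |

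This is clearly better. It would usually reveal a residual as large as the whole effect, but would miss one of half that size more often than not.

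**4. Direction of bias.** Take a true effect of 0.8 SD. In the riboflavin-first sequence, let the residual benefit be r16 at week 16 and r28 at week 28. The pooled estimate averages the two period differences.
- Raw week-28 score: (0.8 + (0.8 - r28))/2 = 0.8 - r28/2. With r28 = 0.4 this is 0.6, toward no effect.
- Change from the week-16 baseline: (0.8 + (0.8 + r16 - r28))/2 = 0.8 + (r16 - r28)/2. With r16 = 0.4, the estimate is 0.8 if r28 = 0.4, 0.9 if r28 = 0.2, and 1.0 if r28 = 0. That is no bias, or bias away from the null.

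**The case against.** The strongest reply is that the plan never makes pooling depend on the test and never says that a non-significant result justifies it. That is correct: no test-then-choose procedure is written, and a reader who infers one goes beyond the text. The gap is an assumption that is pooled on regardless, with one check whose meaning and consequence are unstated.

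Second, a reader might take about 12% as the power of the planned test. The documents do not support a single figure. No statistic is named, and carryover size and correlation are assumptions. The week-16 data allow a better comparison, so it would also be wrong to say that this trial could not detect any relevant carryover.

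Third, a reader might infer that carryover must dilute the pooled estimate. That holds for raw week-28 scores, not for change from the week-16 baseline that Section 6.3 specifies.

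Fourth, on the washout itself, Section 2's statement that riboflavin is not stored is a pharmacological rationale. It concerns the vitamin, not how long plaques stay improved. The survey cannot settle the matter in the other direction. About a third of cards came back (50/156 = 32%), there was no control group, treatment was by injection, partial relapses are counted in the 82%, and not being seen in clinic is not documented time off riboflavin.

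Finally, Section 11 tests equal carryover while the pooling sentence assumes none. This adds no problem, since equal carryover is enough for an unbiased pooled comparison.

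**Conclusion.** The point holds in this form: the pooled estimate rests on an assumed absence of carryover, the documents give no data that four weeks clears the clinical effect, and a non-significant carryover test would not validate the assumption.

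For carryover of half an assumed 0.8 SD effect, power is about 11-15% on totals and 25-44% at week 16. For carryover equal to the whole effect it is 29-45% and 74-95%. The totals-based interval, at ±0.86-1.12 SD, is wider than the assumed effect itself. All of these figures depend on the assumed effect, carryover and correlation.

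The size and sign of bias cannot be fixed from the documents. With a 0.4 SD residual at week 16, a true 0.8 SD could be estimated as anything from 0.6 (raw week-28 scores, residual persisting) to 1.0 (change from week 16, residual gone by week 28). Nothing here shows that carryover will occur. The conclusion is that the plan could not tell the reader whether it had.

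**What to change.** Amend Section 11 as follows:

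1. Replace the pass/fail test with an estimate of carryover and its 95% CI. Include the between-sequence difference in week-16 PASI, adjusted for week 0.
2. State that a non-significant carryover result does not validate pooling.
3. Name the week-12 between-sequence comparison of PASI 50 as the carryover-free sensitivity analysis. Report it beside the pooled result always, whatever the carryover estimate shows.
4. Analyse that comparison with an independent-groups method (Fisher exact or logistic regression). McNemar's test is for paired data, and at week 12 the two sequences are separate groups of subjects.

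No visits, samples or subjects are added; PASI at weeks 0, 12 and 16 is already scheduled. The cost is wording and one more reported analysis, which has lower power than the crossover. On a continuous scale with d = 0.8, the unadjusted week-12 comparison has about 74% power, against 96% or more for the within-subject analysis. The two results may also differ by chance, so the plan should say in advance that the week-12 result is a sensitivity analysis.

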## **7 LABORATORY ASSESSMENTS**

Biopsies will be processed for metabolomic profiling and will be taken from psoriatic normal (PN) as well as psoriatic plaque (PP) skin. Six 6 mm punch biopsies of the skin will be performed on each subject throughout the study. Two PN and two PP biopsies will be performed on week 0. Then one PN and one PP biopsy will be performed at week 12. For each subject, we will attempt to obtain all biopsies from the same plaque and the same area of normal skin. These biopsies will be divided in half and used for RNA profiling and histology.

Histological assessment will be performed for all patients using H&E, proliferation markers (Ki67), keratin 16, human beta defensin 2 (hBD2). Samples will be processed in batches of 10 patients at a time to limit batch-to-batch variation. To determine tissue responses, we will run a total of 20 patients for metabolomic and RNA-seq profiling.

All subjects will have a CBC, CMP drawn on screening and then at weeks 12, and 28. All patients in the study will have plasma measurements of riboflavin and FAD at weeks 0, 2, 12, 18, and 28. This will be a total of approximately 127 mL of whole blood per subject.

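### For biopsy markers, sampled only at weeks 0 and 12, Section 11 names no between-group test that uses the week-0 value; adjusting for it would usually gain precision at almost no cost

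*Combined protocol and SAP*

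**What the plan says.** Section 7 fixes the tissue schedule: "Two PN and two PP biopsies will be performed on week 0. Then one PN and one PP biopsy will be performed at week 12". Sections 6.2 and 6.3 and Table 1 agree, and no biopsy follows week 12. Section 7 also aims to match the sites: "For each subject, we will attempt to obtain all biopsies from the same plaque and the same area of normal skin". Histology is planned for all patients. The omics work is smaller: "To determine tissue responses, we will run a total of 20 patients for metabolomic and RNA-seq profiling".

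Two sentences of Section 11 can reach continuous tissue data:

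- Within sequence: "Differences within each sequence of treatment from baseline to endpoint will be assessed using parametric general linear models such as the paired t-test".
- Between groups: "Parametric t-tests will be used to determine if continuous laboratory assessments are significantly different between the treatment groups".

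The first uses baseline but does not compare riboflavin with placebo. The second makes that comparison but does not say whether the week-0 value enters. Section 11 also sends ordinal assessments to a Wilcoxon signed rank test. Sections 3.1 and 3.2 list no tissue marker as an endpoint.

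**The concern.** Crossover pooling cannot help here, because no subject has tissue from both treatments. The randomised tissue comparison is between two parallel groups, and the trial already holds a matched week-0 value for each subject. If that value predicts the week-12 value, leaving it out of the comparison keeps between-subject variation in the error term that could be removed.

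The groups are small: 44 subjects at the planned size for histology, and 20 in total for omics. Power for a true tissue response is limited. A plan whose only baseline-based method is the within-sequence test also makes it tempting to read a tissue effect from an uncontrolled before-and-after change.

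**Working it through.** **Inputs from the plan.** Two-sided alpha 0.05 (Section 11); 22 per sequence (Section 11); 20 omics patients in total (Section 7).

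**Assumed, because the plan is silent.** A 10/10 split of the omics patients; normally distributed markers with equal SD at both visits; d = 0.8 in SD units of the week-12 value; correlation rho = 0.5, range 0 to 0.7. Section 11 describes its inputs only in words: "Assuming a large effect size and a conservative amount of correlation between the measurements".

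**The plan's own figure.** Section 11 states that "a sample size of 22 subjects in each sequence yields a statistical power of 80" per cent. This is the general sample-size statement, not one for tissue. Without a numerical effect size or correlation it cannot be reproduced uniquely. At d = 0.8 a parallel t-test with 22 per group gives 73.6% and needs 25 to 26 per group for 80%. A crossover t-test on 44 subjects gives 95.6% at rho = 0. It therefore cannot be used to infer the rho the authors had in mind.

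**Variance of the estimated treatment difference (SD = 1, n per group).**

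- t-test on the week-12 value: 2/n, with 2n − 2 df.
- t-test on change: 2(1 − rho) × 2/n, with 2n − 2 df. The factor 2(1 − rho) is 1.4 at rho 0.3, 1.0 at 0.5 and 0.6 at 0.7.
- ANCOVA: (1 − rho²) × (2/n + D²/Sxx), with 2n − 3 df. D is the chance difference in week-0 means and Sxx the pooled within-group sum of squares. On average the D term multiplies 2/n by 1 + 1/(2n − 4): 1 + 1/16 = 1.063 for n = 10 and 1 + 1/40 = 1.025 for n = 22.

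At rho = 0.5 the ANCOVA variance relative to the plain t-test averages 0.75 × 1.063 = 0.80 (n = 10) or 0.75 × 1.025 = 0.77 (n = 22). The change score has a ratio of exactly 1.

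**Power from the noncentral t distribution, averaged over D for ANCOVA, d = 0.8.**

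| n per group | rho | t-test, week 12 | t-test, change | ANCOVA | ANCOVA minus week-12 t-test (points) |
|---|---|---|---|---|---|
| 10 | 0 | 39.5% | 22.4% | 37.6% | −1.9 |
| 10 | 0.3 | 39.5% | 29.9% | 40.6% | +1.1 |
| 10 | 0.5 | 39.5% | 39.5% | 47.4% | +7.9 |
| 10 | 0.7 | 39.5% | 58.9% | 63.2% | +23.7 |
| 22 | 0 | 73.6% | 45.0% | 72.6% | −1.0 |
| 22 | 0.3 | 73.6% | 59.1% | 76.5% | +2.9 |
| 22 | 0.5 | 73.6% | 73.6% | 84.0% | +10.4 |
| 22 | 0.7 | 73.6% | 91.7% | 94.8% | +21.2 |

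Simulation (20,000 trials per setting) at rho = 0.5 agrees: 39.7% to 47.8% with 10 per group, and 73.7% to 83.8% with 22.

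**Other checks.** With 10 per group and d = 1.0, power goes from 56.2% to 65.8% at rho 0.5 and to 53.6% at rho 0, a loss of 2.6 points. Under no effect, a separate simulation (6,000 trials per setting) gave rejection rates of 4.8% to 5.6% across the three methods.

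**Break-even.** Ignoring the lost degree of freedom, ANCOVA gains once (1 − rho²) × 1.063 < 1, that is rho above about 0.24 for n = 10. For n = 22 the condition is (1 − rho²) × 1.025 < 1, or rho above about 0.16.

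**The case against.** The strongest reply is that this is an efficiency preference on exploratory data. Most of its limits stand:

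- **A reader might infer that the plan discards the week-0 biopsy.** The documents do not say so. Section 11 is silent on whether the tested quantity is the week-12 value or the change. A change-score reading would use week 0, but it gains nothing at rho 0.5, is worse than the plain t-test at 0.3, and falls below ANCOVA in every row of the table.
- **A reader might infer that the t-test is invalid or biased.** It is neither. Type I error is about 5%, and chance imbalance is already reflected in its standard error.
- **The quoted sentence may be aimed at plasma riboflavin and FAD**, the only laboratory endpoint in Section 3.2. Extending it to tissue is reasonable because Section 7, on laboratory assessments, specifies the biopsies, but it is not explicit. Any histology marker scored ordinally would fall under the Wilcoxon sentence instead.
- **A reader might apply the 10-per-group figures to the omics data.** They concern one marker tested at 0.05. As an illustration, at an assumed threshold of 0.0005 with d = 1.0 and rho 0.5, power is about 5.5% for the t-test and 8% for ANCOVA. Adjustment does not rescue that analysis.
- **The correlation is unknown.** Same-site sampling is attempted, not guaranteed, and Section 7 does not say that both week-0 plaque samples receive the same assay.

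None of this supplies a reason to leave the between-group tissue analysis without a stated role for a value that is already collected.

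**Conclusion.** The point holds as a cheap gain in precision. For continuous biopsy markers, Section 11 names no between-group analysis that uses the week-0 value, although the design provides one for each subject. With d = 0.8 and rho = 0.5, both assumed, the cost is about 8 points of single-marker power with 10 per group and about 10 with 22. The size depends heavily on rho: small at 0.3, large at 0.7, and slightly negative near zero. The primary result and the listed secondary endpoints are unaffected.

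**What to change.** In Section 11, separate biopsy outcomes from the general laboratory t-test sentence and state that:

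- Biopsy outcomes exist in period 1 only and are compared between riboflavin and placebo as parallel groups.
- Each continuous marker's week-12 value is analysed by ANCOVA with treatment and the subject's own week-0 value from the same tissue type, using the mean of the two week-0 samples where both are assayed. Plaque and normal skin are analysed separately.
- Within-sequence changes are descriptive.
- Metabolomic and RNA-seq features use a per-feature model that includes the week-0 value, with a named multiplicity procedure.
- A stated rule covers subjects with no usable week-0 sample.

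The plan should also say which histology markers are continuous and which are ordinal. The cost is a short paragraph of text and one degree of freedom per model. No further biopsies, assays or patients are needed.

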### 3 OBJECTIVES

#### 3.1 Primary endpoint

The number of subjects that achieve a 50 percent or greater reduction in their PASI with intervention as compared to placebo.

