#### 3.2 Secondary endpoints

- The number of subjects that achieve a PASI 75, 90, 100 response with intervention as compared to placebo.
- The number of subjects that achieve a PGA score of 0/1 with intervention as compared to placebo.
- The number of subjects that report a pruritus score of 0/1 with intervention as compared to placebo.
- The number of subjects treated that report a DLQI score of 0/1 with intervention as compared to placebo.
- The difference in serum plasma levels of riboflavin and FAD in subjects treated with intervention as compared to placebo.

[figure not shown]

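### Section 11 sets an 'overall' alpha of 0.05, but nothing in the plan makes it overall across one primary and eight secondary comparisons, so the status of the secondary p-values is undefined

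*Combined protocol and SAP*

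**What the plan says.** Section 11 states one significance rule for the trial: "An overall alpha-level of 0.05 will be used to determine statistical significance and all statistical tests will be two-sided". No other level appears.

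Section 3.1 has one primary endpoint: "The number of subjects that achieve a 50 percent or greater reduction in their PASI with intervention as compared to placebo".

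Section 3.2 has five bullets, which contain eight comparisons with placebo:

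- three PASI thresholds: "The number of subjects that achieve a PASI 75, 90, 100 response with intervention as compared to placebo"
- global assessment: "The number of subjects that achieve a PGA score of 0/1 with intervention as compared to placebo"
- itch: "The number of subjects that report a pruritus score of 0/1 with intervention as compared to placebo"
- quality of life: "The number of subjects treated that report a DLQI score of 0/1 with intervention as compared to placebo"
- two plasma levels: "The difference in serum plasma levels of riboflavin and FAD in subjects treated with intervention as compared to placebo"

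Neither the synopsis, Section 3 nor Section 11 gives a hierarchy, a gate on the primary result, a split of alpha or a multiplicity correction. Nothing labels the secondary p-values nominal or exploratory. Section 11 also describes several analyses (change within each sequence, a week-12 McNemar comparison, a pooled crossover estimate) without saying which one is the test of PASI 50.

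**The concern.** The word 'overall' can be read in two ways, and the plan is incomplete under both.

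- **Family-wise rate.** The sentence then promises at most a 5% chance of any false positive across the comparisons, but no rule says how the 5% is shared or ordered. The plan cannot be carried out as written.
- **General threshold.** Each comparison is then judged at 0.05 regardless of PASI 50, and no overall rate is controlled.

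What is at stake is the claim the trial may make if PASI 50 fails. An isolated p below 0.05 on itch or DLQI could be reported as statistically significant under the plan's own sentence. That matters here because Section 2 describes earlier case series that point in opposite directions, and the trial is small.

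**Working it through.** **Inputs from the documents.** Level 0.05, two-sided (Section 11). One primary and eight secondary comparisons, six of them clinical (Section 3). Sample size: "a sample size of 22 subjects in each sequence yields a statistical power of 80" percent, so N = 2 × 22 = 44. McNemar is named for dichotomised endpoints, without saying exact or chi-square. No response rates or correlations are given, so these are assumed below.

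**Step 1: the plan's own figure.** With one test at 0.05 the error rate is 1 − 0.95 = 0.05. The stated level is reproduced if it refers to PASI 50 alone.

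**Step 2: independent tests, for reference only.** If k true nulls are each tested at 0.05, P(at least one rejection) = 1 − 0.95^k.

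- Six clinical secondaries: 1 − 0.95^6 = 0.265.
- All eight: 1 − 0.95^8 = 0.337.

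These are not realistic here. PASI 75, 90 and 100 are nested cuts of one score, the clinical scores are likely to be correlated, and exact McNemar is conservative when few pairs are discordant.

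**Step 3: dependent tests.** Crossovers with no treatment effect were simulated: 44 subjects, nested PASI cuts, correlation 0.5 between endpoints and 0.5 within subject across periods, each test at 0.05, 20,000 runs. The two plasma tests were given correlation 0.5 with each other and were independent of the clinical ones. The table shows the chance of at least one p < 0.05.

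| Assumed response, % (PASI 75 / 90 / 100 / PGA / itch / DLQI) | Six clinical, exact | Six clinical, chi-square | All eight, exact | All eight, chi-square |
|---|---|---|---|---|
| Low: 5 / 2 / 1 / 5 / 15 / 10 | 3.6% | 15.1% | 12.1% | 22.5% |
| Mid: 25 / 12 / 5 / 25 / 30 / 25 | 10.8% | 21.3% | 19.0% | 28.6% |
| High: 45 / 30 / 15 / 40 / 40 / 40 | 13.3% | 22.7% | 21.2% | 29.7% |

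A second set of simulations used the same correlations and other assumed rates. For the six clinical secondaries, exact McNemar gave 1.0% when rates ran from 0.5 to 5%, 3.1% for 1 to 10%, 6.4% for 2 to 15% and 9.7% for 5 to 25%. Chi-square gave 12 to 22%.

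**Step 4: lower end for all eight.** The low row implies that the two plasma tests contribute 1 − (1 − 0.121)/(1 − 0.036) = 0.088. With the smallest clinical figure, 1 − (1 − 0.010)(1 − 0.088) = 0.097, or about 10%.

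**Step 5: the remedies.** With PASI 50 alone declared at 0.05, the confirmatory error rate is 0.05. With a gate, if PASI 50 has no effect, any false secondary claim first needs a false PASI 50 rejection, so the chance is at most 0.05. If PASI 50 has a real effect, Holm on the six clinical secondaries (first step 0.05/6 = 0.0083) holds their family-wise rate to at most 0.05. The PASI 50 test and its sample size are unchanged.

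**The case against.** The strongest reply is that the plan does not contradict itself. Section 11 never says that each test is run at 0.05, nor that secondaries are judged whatever PASI 50 shows. If 'overall' means family-wise, the achieved rate is undefined rather than wrong. If it means the general threshold, no family-wise rate was promised. A mismatch appears only if the word is read one way for the promise and the other way for the tests. This stands. The defect is a missing rule, not a stated rate shown to be false. Testing at 0.05 is an inference, though the likeliest one because no other level is given.

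It can also be said that PASI 50 is the only objective the synopsis words as showing superiority, so the secondaries are descriptive support. That is reasonable, but the plan does not say so, and Section 11 uses significance language for laboratory assessments as well.

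On size, exact McNemar with low response rates keeps the six clinical secondaries below 5%. That also stands, but Section 11 does not commit to the exact version. The simulations pair each subject's two periods, whereas Section 11 attaches McNemar to a week-12 comparison of the sequences, so the test simulated may not be the test intended.

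Two stronger readings are tempting, and the documents support neither. A reader might infer that the primary conclusion carries an inflated error rate; it does not, because there is one primary endpoint and the secondaries add nothing to its error. A reader might also cite 26% or 34% as the rate the plan delivers; those figures need independent tests, which nested PASI cuts rule out.

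**Conclusion.** The point holds as a gap in the decision rule for secondary endpoints. Nothing in the plan makes 0.05 an overall rate, and as written a secondary result could be called significant after PASI 50 fails.

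If every secondary is tested at 0.05 and none has an effect, the chance of at least one false positive is about 1 to 13% (exact) or 12 to 23% (chi-square) for the six clinical endpoints, and roughly 10 to 30% for all eight. These ranges rest on assumed response rates and correlations, N = 44 and one analysis per endpoint; they illustrate and are not bounds. The six-endpoint figures are the more relevant, since the plasma levels mainly show whether subjects were exposed to riboflavin.

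This should be settled before unblinding. It limits what may be claimed from secondary results and leaves the validity of the PASI 50 test untouched.

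**What to change.** In Section 11:

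1. Name the one analysis, among those listed, that tests PASI 50. Alpha cannot be assigned to a test that is not identified.
2. Replace the 'overall' wording with a statement that two-sided 0.05 applies to that single PASI 50 comparison.
3. State that all secondary p-values are nominal, are reported with confidence intervals and are not called statistically significant.

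If the sponsor wants confirmatory secondary claims, item 3 can be replaced by a gate: test the six clinical secondaries only if PASI 50 is significant, using Holm at 0.05 or a fixed order that the sponsor specifies in advance. The documents do not point to a particular order, so that choice is the sponsor's. Plasma riboflavin and FAD would stay outside the family as exposure checks.

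Items 2 and 3 take a sentence or two. Item 1 needs a decision as well as wording. No visits, data or subjects are added. The downside is that fewer secondary results can be called significant.
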